^f Fremanezumab at 675 mg sc at visit 2 (week 0) of the pivotal study and fremanezumab at 225 mg sc at visits 3 and 4 (weeks 4 and 8, respectively) of the pivotal study.

CCH=chronic cluster headache; ECH=episodic cluster headache; IMP=investigational medicinal product; iv=intravenous; sc=subcutaneous.

Patients with a diagnosis of ECH who experience CH remission, defined as no CH attacks for 12 successive weeks at any time after starting IMP (ie, administration of the first dose of IMP in the pivotal study), will be offered the possibility to stop treatment and continue to attend the

subsequent scheduled visits. If treatment is stopped and CH attacks resume within 12 weeks after stopping treatment, patients will restart treatment at their previous dose regimen through week 36. If treatment is stopped and CH attacks resume after more than 12 weeks after stopping treatment, patients will restart fremanezumab treatment at 675 mg sc quarterly through week 36.

Patients with a diagnosis of CCH who experience CH remission, defined as no CH attacks for 24 successive weeks at any time after starting IMP (ie, administration of the first dose of IMP in the pivotal study), will be offered the possibility to stop treatment and continue to attend the subsequent scheduled visits. If treatment is stopped and CH attacks resume within 12 weeks after stopping treatment, patients will restart fremanezumab treatment at 225 mg sc monthly through week 36. If treatment is stopped and CH attacks resume after more than 12 weeks after stopping treatment, patients will restart fremanezumab treatment with a 675-mg sc loading dose followed by 225-mg sc monthly through week 36. After 15 June 2018, only patients who participated in the ECH study (Study TV48125-CNS-30056) will be enrolled for active treatment. All CCH patients included in this study have been asked to discontinue treatment and are encouraged to continue in the ADA and safety follow-up portion of this study.

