The study duration will be for approximately 42 months, from Q1/2017 to Q2/2020.

The study schematic diagram for patients enrolling in this study for the purpose of evaluating the long-term safety and efficacy of fremanezumab is presented in [Figure 1](#).

Figure 1: Overall Study Schematic Diagram

Clinical Study Protocol with Amendment 04

- ^a As of 15 June 2018, only patients from the ECH study (Study TV48125-CNS-30056) will enroll in this study. As of 15 June 2018, all CCH patients included in this study have been asked to discontinue treatment, and are encouraged to continue in the ADA and safety follow-up portion of this study. At the time of unblinding the treatment code in Study TV48125-CNS-30057 (planned for Q4 2018), those CCH patients who were receiving placebo in Study TV48125-CNS-30057 (ie, never received any study drug) will not be required to complete additional safety follow-up visits, and will be discharged from the study.
- ^b The run-in period for patients with ECH lasted at least 7 days (+3 days), and the run-in period for patients with CCH lasted at least 28 days (+3 days).
- ^c Screening will occur at visit 1 of the Phase 3 pivotal efficacy studies. After 15 June 2018, only patients who participated in the ECH study (Study TV48125-CNS-30056) will be enrolled for active treatment.
- ^d Visit 1 of this study corresponds to the EOT visit (visit 5) of the pivotal efficacy studies. The EOT visit procedures/assessments for the pivotal efficacy study must be completed before beginning visit 1 procedures/assessments. EOT visit procedures/assessments will not be repeated at visit 1 of this study. The EOT visit procedures/assessments are detailed in the protocols for Studies TV48125-CNS-30056 and TV48125-CNS-30057.
- ^e Visit 11 corresponds to Visit 1 for the ADA and Safety follow-up portion of this study.

ADA=anti-drug antibody; CCH=chronic cluster headache; ECH=episodic cluster headache; EOT=end-of-treatment; iv=intravenous; pts=patients; sc= subcutaneous; V=visit; W=week.

Note: Up to 600 patients from the Phase 3 pivotal efficacy studies (Studies TV48125-CNS-30056 and TV48125-CNS-30057) are expected to enroll in this study.

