Return electronic diary device											X	
Blood sample for pharmacokinetics analysis ^f		X	X	X	X	X	X	X	X	X	X	
Blood sample for serum ADA analysis ^s				X			X			X	X	X
Blood collection for serum, plasma, and RNA biomarker analysis ^t				X			X			X	X	X
Urine collection for biomarker analysis				X			X			X	X	X
HADS ^p		X					X			X	X	
EQ-5D questionnaire ^p		X					X			X	X	
SF-12 ^p		X					X			X	X	
WPAI questionnaire ^p		X		X			X			X	X	
Impact on Partners and Family questionnaire ^{p,u}		X		X			X			X	X	
PPSI ^v		X	X	X			X			X	X	
PGIC scale ^v		X	X	X			X			X	X	
Wearable sensor substudy data capture ^w	X										X	

Table 4: Study Procedures and Assessments for Treated Patients (Continued)

	Double-blind treatment period ^a											Follow-up period
Visit number	V1 ^b	V2	V3	V4	V5	V6	V7	V8	V9	V10	V11	V12
Procedures and assessments (completed before dosing, when applicable, unless otherwise noted)	Week 0 (day 0)	Week 4 (±3 days)	Week 8 (±3 days)	Week 12 (±3 days)	Week 16 (±3 days)	Week 20 (±3 days)	Week 24 (±3 days)	Week 28 (±3 days)	Week 32 (±3 days)	Week 36 (±3 days)	EOT/early withdrawal week 40 (±3 days)	Follow-up week 68 (±1 week) ^c
Wearable sensor check and compliance check		X	X	X	X	X	X	X	X	X	X	
Return wearable sensor											X	
Study IMP administration ^x	X	X	X	X	X	X	X	X	X	X		
Injection site reaction/pain assessment ^y	X	X	X	X	X	X	X	X	X	X		
Anaphylaxis and hypersensitivity reaction assessment ^z	X	X	X	X	X	X	X	X	X	X		

^a An unscheduled visit may be performed at any time during the study at the patient’s request and as deemed necessary by the investigator. The date and reason for the unscheduled visit will be recorded on the CRF as well as any other data obtained from procedures and assessments.

^b Visit 1 of the current study corresponds with the EOT visit (visit 5) of the pivotal efficacy studies. EOT visit procedures/assessments must be completed before the patient begins participation in this study, and the EOT procedures/assessments will not be repeated at visit 1 of this study. The EOT visit procedures/assessments are detailed in the protocols for Studies TV48125-CNS-30056 and TV48125-CNS-30057.

^c For patients who discontinue the study early and patients who achieve CH remission (ie, meaning they stop and may restart treatment depending upon whether or not CH attacks recur), the follow-up visit will be approximately 7.5 months after the last dose of IMP.

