- ADA=antidrug antibody; β-HCG=beta-human chorionic gonadotropin; CCH=chronic cluster headache; CH=cluster headache; CRF = case report form; ECG=electrocardiogram; ECH=episodic cluster headache; eC-SSRS=electronic Columbia-Suicide Severity Rating Scale; EOT=end-of-treatment; EQ-5D=EuroQol-5 Dimension; HADS=Hospital Anxiety and Depression Scale; IMP=investigational medicinal product; n/a=not applicable; PGIC=Patient Global Impression of Change; PPSI=Patient-Perceived Satisfactory Improvement; sc=subcutaneous; SF-12=12-Item Short-Form Health Survey; V=visit; WOCBP=women of childbearing potential; WPAI=Work Productivity and Activity Impairment.

Table 5: Study Procedures and Assessments for Patients Rolling Over from the Pivotal Efficacy Studies for Evaluation of Antidrug Antibodies and Safety (Adverse Events and Concomitant Medications) Only

Procedures and assessments	Enrollment visit	Follow-up visit
	Visit 1 ^a	Visit 12
	Day 0	Approximately 7.5 months (approximately 5 half-lives of the IMP) after the last dose of the IMP during the pivotal efficacy study
Informed consent	X	
Adverse events ^b	X	X
Concomitant medication inquiry	X	X
Blood sample for ADA analysis		X

^a Visit 1 of the current study corresponds with the EOT visit/early withdrawal visit of the pivotal efficacy studies. EOT visit procedures/assessments must be completed before the patient begins participation in this study. The EOT visit procedures/assessments are detailed in the protocols for Studies TV48125-CNS-30056 and TV48125-CNS-30057.

^b Patients will return for unscheduled visits in the event of any safety concern.
ADA=antidrug antibody; EOT=end-of-treatment; IMP=investigational medicinal product.

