Procedures for patients who withdraw prematurely from the study are described in [Section 4.3](#). Patients should be treated with standard of care after termination of the study as appropriate.

Patients with ongoing adverse events or clinically significant abnormal laboratory test results (as interpreted by the investigator) will be monitored as described in [Section 7.1.2](#).

4. **Unscheduled Visits**

An unscheduled visit may be performed at any time during the study, at the patient's request or as deemed necessary by the investigator. The date and reason for the unscheduled visit will be recorded on the case report form as well as any other data obtained (eg, adverse events, concomitant medications and treatments, and results from procedures or tests).

Procedures performed during unscheduled visits include the following:

- Review electronic diary data (if applicable).
- Review study compliance.
- Perform vital signs measurements (including systolic and diastolic blood pressure, pulse, and body temperature).
- Inquire about adverse events.
- Inquire about concomitant medications.
- Complete the eC-SSRS Since Last Visit version.

Other procedures may be performed at the discretion of the investigator.

Patients Enrolling in This Study for Evaluation of Antidrug Antibodies and Safety (Adverse Events and Concomitant Medications)

1. **Visit 1**

The following procedures/assessments will be performed at visit 1 for patients who enroll in this study for the purpose of evaluating ADAs, and safety (adverse events and concomitant medications):

- Obtain written informed consent before any other study-related procedures are performed.
- Inquire about adverse events.
- Inquire about concomitant medications.

2. **Follow-up Visit (Visit 12 – Approximately 7.5 months after the last dose of IMP during the pivotal efficacy study)**

Patients enrolling in this study for the purpose of evaluating ADAs and safety (adverse events and concomitant medications) only will attend a visit approximately 7.5 months after receiving the last dose of IMP (during the pivotal efficacy studies). The following procedures/assessments will be performed at this visit:

- Inquire about adverse events.
- Inquire about concomitant medications.
- Obtain a 5-mL blood sample for ADA analysis.

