4.4. Study Days and Visits

For by-visit summaries, if there are multiple assessments at a postbaseline visit then the last non-missing assessment at that visit will be used for the summary (this includes scheduled and unscheduled assessments), except for triplicate ECG assessments (see Section 8.11 for further details).

Study visits for patients who are enrolled the study for full study assessments are in Table 2. Study procedures and assessments are detailed in the Table 4 of the study protocol.

Table 2: Study Visits for Treated Patients

Double-blind treatment period							Follow-up period					
Visit #	V1	V2	V3	V4	V5	V6	V7	V8	V9	V10	V11	V12
Week	0	4	8	12	16	20	24	28	32	36	40	68
											EOT/early withdrawal	

Notes: Visit 1 of the current study corresponds with the EOT visit (visit 5) of the pivotal efficacy studies. The EOT visit procedures/assessments are detailed in the protocols for Studies TV48125-CNS-30056 and TV48125-CNS-30057. EOT=end of treatment.

Study visits and assessments for patients who are enrolled in the study for the purpose of evaluating ADAs and safety only are detailed in Table 3.

Table 3: Study Visits and Assessments for Patients Enrolled in the Study for Evaluation of Antidrug Antibodies and Safety (Adverse Events and Concomitant Medications) Only

Procedures and assessments	Enrollment visit	Follow-up visit		
	Visit 1 ^a	Visit 12		
	Day 0	Approximately 7.5 months (approximately 5 half-lives of the IMP) after the last dose of the IMP during the pivotal efficacy study		
Informed consent	X			
Adverse events b	X	X		
Concomitant medication inquiry	X	X		
Blood sample for ADA analysis		X		

^a Visit 1 of the current study corresponds with the EOT visit/early withdrawal visit of the pivotal efficacy studies. EOT visit procedures/assessments must be completed before the patient begins participation in this study. The EOT visit procedures/assessments are detailed in the protocols for Studies TV48125-CNS-30056 and TV48125-CNS-30057.

Study days are numbered relative to the first day of the IMP administration in this study. The start of treatment (day 1) is defined as the date on which a patient takes the first dose of the IMP in this study, as recorded on the case report form (CRF). Days will be numbered relative to treatment start (ie, ..., -2, -1, 1, 2, ...; with day 1 being the first day of the IMP administration and day -1 being the day before the first day of the IMP administration).

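### Table 5, Appendix B and SAP Table 3 count visit 12 from the last pivotal-study dose and were not adapted for chronic cluster headache (CCH) patients already dosed in this study; other passages give different dates, and none says which governs

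*Protocol*

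**What the plan says.** Protocol Section 3.5 assigns two schedules by purpose of enrolment. Table 4 is for patients who enrol for treatment. Table 5 is titled for "Patients Rolling Over from the Pivotal Efficacy Studies for Evaluation of Antidrug Antibodies and Safety (Adverse Events and Concomitant Medications) Only". It has an enrolment visit and one later visit, visit 12, which carries the table's single ADA sample. Visit 12 is timed at "Approximately 7.5 months (approximately 5 half-lives of the IMP) after the last dose of the IMP during the pivotal efficacy study". Appendix B repeats the anchor: "7.5 months after receiving the last dose of IMP (during the pivotal efficacy studies". SAP Section 4.4, Table 3 does the same: "after the last dose of the IMP during the pivotal efficacy study".

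After the CCH pivotal study was terminated, Section 3.1 states that CCH patients in this study were asked to stop treatment and "are encouraged to continue in the ADA and safety follow-up portion of this study". The same section refers patients in safety follow-up to Table 5. Figure 1, footnote e adds: "Visit 11 corresponds to Visit 1 for the ADA and Safety follow-up portion of this study".

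Other current text gives different dates:

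- Table 4 footnote c, for patients who leave the study early or reach remission: "the follow-up visit will be approximately 7.5 months after the last dose of IMP".
- The synopsis (early withdrawals), Section 9.1 (patients offered treatment) and Appendix B (patients who stop treatment and also withdraw) all use 7.5 months from the last dose of IMP, without restricting it to the pivotal study.
- Section 3.1 gives early withdrawals 7.5 weeks where the synopsis gives 7.5 months.
- Appendix B, for patients who stop treatment but keep attending, labels visit 11 as week 36 and visit 12 as week 40. Table 4 has them at weeks 40 and 68.

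**The concern.** Table 5 expresses the wait before visit 12 in half-lives, so its evident purpose is to let drug clear before the final ADA sample and to extend the adverse event inquiry over that period. The pivotal-dose anchor serves that purpose for someone who was never dosed here. It does not for a CCH patient who received up to ten doses in this study, because the clock started before the first of them. For a CCH patient on placebo in the pivotal study who then began fremanezumab here, the anchor would be a placebo injection.

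The change list for Amendment 04 updates Figure 1 and Section 7.8 but has no entry for Table 5 or Appendix B. A site that follows Section 3.1 to Table 5 could therefore draw the late sample, and hold the last safety inquiry, with substantial drug still present. ADA incidence and kinetics are stated endpoints and long-term safety is the primary objective. Protocol Section 2.1 says data from CCH patients enrolled before 15 June 2018 count towards all objectives.

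**Working it through.** **Inputs.** Visit 12 at 7.5 months (Table 5). Last pivotal dose at pivotal week 8 (Table 3 footnotes). Pivotal end-of-treatment visit equals visit 1 here (Table 5 footnote a). Pivotal length 3 months (Section 1.2.1), taken as week 12; this is an assumption. CCH dosing every 4 weeks, weeks 0 to 36 (Section 5.1.1.1). Mean half-life 32.2 to 36.2 days (Section 1.2.2.1).

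**The plan's own figures.** 7.5 × 30.44 = 228 days = 32.6 weeks. Five half-lives at the stated values are 5 × 32.2 = 161 to 5 × 36.2 = 181 days, or 5.3 to 5.9 months. So 7.5 months is 228/36.2 = 6.3 to 228/32.2 = 7.1 half-lives. Exactly five would need 228.3/5 = 45.7 days. The description of 7.5 months as about five half-lives is not reproduced from the stated half-life, so both bases are carried below. Separately, week 36 + 32.6 = week 68.6, inside Table 4's week 68 ± 1. For patients who complete dosing, Table 4 therefore counts from the last dose in this study.

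**Literal Table 5 date.** The last pivotal dose is at week 8 − 12 = −4 of this study. Visit 12 is then at −4 + 32.6 = week 28.6, or day 200. With 28-day months (210 days) it would be week 26.0.

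**Gap and residual.** For a last dose at week W, gap = 200 − 7W days and fraction remaining = 2^(−gap / half-life).

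| Last dose here (week) | Gap (days) | Half-lives (36.2 to 32.2 d) | Remaining (32.2 to 36.2 d) | Remaining (45.7 d) |
|---|---|---|---|---|
| 0 | 200 | 5.5-6.2 | 1-2% | 5% |
| 4 | 172 | 4.8-5.4 | 2-4% | 7% |
| 8 | 144 | 4.0-4.5 | 4-6% | 11% |
| 12 | 116 | 3.2-3.6 | 8-11% | 17% |
| 16 | 88 | 2.4-2.7 | 15-18% | 26% |
| 20 | 60 | 1.7-1.9 | 27-32% | 40% |
| 24 | 32 | 0.9-1.0 | 50-54% | 61% |
| 28 | 4 | 0.1 | 91-92% | 94% |
| 32 | −24 | visit precedes dose | – | – |

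For comparison, 228 days after the last dose leaves about 1% at the stated half-life, or 3% at 45.7 days.

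**The other readings.** Counted from the last dose of IMP, the gap is 228 days whatever W is. Under the 7.5 weeks of Section 3.1 it is 52.5 days, or 52.5/36.2 = 1.5 to 52.5/32.2 = 1.6 half-lives (1.1 at 45.7 days).

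**The case against.** The strongest reply is that Table 5 does not cover these patients. Section 3.5 assigns tables by purpose of enrolment, the Table 5 title is restricted to patients enrolled for ADA and safety alone, and its visit 1 is the pivotal end-of-treatment visit. SAP Section 4.4 splits its tables in the same way. CCH patients dosed here enrolled for treatment, so Table 4 and its footnote c would apply, and four places count from the last dose of IMP.

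Much of this stands. A reader might infer that these CCH patients would necessarily be sampled too early. The documents do not support that, because a coherent reading with a full 7.5-month gap exists.

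It does not remove the conflict. Section 3.1 sends safety follow-up patients to Table 5, and Figure 1 footnote e gives the follow-up portion its own visit 1, which Table 4 does not have. The passages that use the last dose of IMP are worded for patients who leave the study early, withdraw, reach remission, or are offered the treatment course. The moved CCH patients stop treatment but stay in the study. For patients who do that, Appendix B gives visit 12 the label week 40.

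Two further points stand. Patients dosed here also have Table 4 ADA samples at visits 4, 7, 10 and 11 or early withdrawal, as far as they reached them, so Table 5's sample is not their only one. A reader might also infer that ADA incidence is biased downward. That depends on the assay's drug tolerance, which is not given.

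**Conclusion.** The protocol gives incompatible dates for the same visit and does not say which applies to CCH patients dosed in this study. Followed literally, the Table 5 date is close to adequate for last doses at weeks 0-4, clearly short from about week 12, under or about one half-life at week 24, and impossible at week 32. A patient last dosed at week 36 has completed scheduled dosing and falls under Table 4's week 68 visit. At risk are the late washout sample and the late safety inquiry.

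The sizes rest on a pivotal end-of-treatment visit at week 12, first-order elimination, and a half-life from single doses in healthy subjects. The mismatch with five half-lives is a failure to reproduce that description from these documents and does not show that 7.5 months is wrong. The number of CCH patients affected and the weeks at which they stopped are not given, so no effect on ADA results can be quantified.

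**What to change.** Reconcile Table 5, both parts of Appendix B, SAP Table 3, Section 3.1, Section 9.1, the synopsis and Table 4 footnote c. State in one place which schedule, and which last dose, govern visit 12 for CCH patients dosed in this study. Limit the pivotal-dose anchor in Table 5, Appendix B and SAP Table 3 to patients not dosed here. The same edit must resolve the 7.5 weeks in Section 3.1 and the week labels for visits 11 and 12 in Appendix B; otherwise the visit still has more than one date.

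The cost is a clause in each affected place. No visit or sample is added, although visit 12 may fall later for some patients than the literal Table 5 date.

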4.1. Patient Inclusion Criteria

Patients may be included in the treatment portion of the study only if they meet all of the following criteria:

- a. The patient is a male or female and 18 to 70 years of age, inclusive, at the start of the pivotal study.
- b. The patient signs and dates the informed consent document.
- c. The patient completes either the Phase 3 pivotal study for ECH (Study TV48125-CNS-30056) or the Phase 3 pivotal study for CCH (Study TV48125-CNS-30057) without important protocol deviations related to patient safety and patient compliance and at least 75% diary data completion during the pivotal study. Prior to 15 June 2018, patients from the ECH study and the CCH study were enrolled. After 15 June 2018, only patients who participated in the ECH study (Study TV48125-CNS-30056) will be enrolled for active treatment.
 - In addition, patients who do not complete the pivotal efficacy studies, and patients who complete the pivotal efficacy studies but do not wish to continue treatment during this long-term safety study, will be offered to enroll in this study for the purpose of evaluating ADAs and safety (adverse events and concomitant medications) approximately 7.5 months after administration of the last dose of the IMP.
- d. Women may be included only if they have a negative beta-human chorionic gonadotropin (β -HCG) test at visit 1, are sterile or postmenopausal, and are not lactating (not applicable for patients participating in safety follow-up only). Definitions of sterile and postmenopausal are given in [Appendix E](#).
- e. Women of childbearing potential (WOCBP) whose male partners are potentially fertile (ie, no vasectomy) must use highly effective birth control methods (see [Appendix E](#)) for the duration of the study and for 7.5 months after discontinuation of IMP.

Men must be sterile or, if they are potentially fertile/reproductively competent (not surgically [eg, vasectomy] or congenitally sterile), and their female partners are of childbearing potential, must agree to use, together with their female partners, acceptable birth control methods for the duration of the study and for 7.5 months after administration of IMP.

Definitions of women of non-childbearing potential, sterile and postmenopausal women; male contraception; and highly effective and acceptable birth control methods, including examples, are given in [Appendix E](#).

- f. The patient must be willing to stop concomitant medications used in clinical practice for the prevention of CH (ie, verapamil, topiramate, valproate, lithium, or methysergide) for the duration of this study. Patients must begin tapering these preventive medications as soon as they begin this study. The period of time needed to taper off these medications will be based on the investigator's medical judgment but should not exceed 1 month from the beginning of participation in this study ([Appendix H](#)) (not applicable for patients participating in safety follow-up only).
- g. The patient is in good health in the opinion of the investigator, as determined by a medical and psychiatric history; medical examination; 12-lead ECG; and serum chemistry, hematology, coagulation, and urinalysis (not applicable for patients participating in safety follow-up only).
- h. The patient must be willing and able to comply with study restrictions to remain at the clinic for the required duration during the study period and to return to the clinic for the follow-up evaluations, as specified in this protocol.

